### **10.2.1 Variable**

The main variables are the peripheral blood Treg% (or other immunoregulatory cells) and mRNA AR signatures seen prior to and during either successful (no rejection) vs. failed (rejection) TAC-WD/EVL.

### **10.2.2 Statistical hypothesis, model, and method of analysis**

The statistical analysis of the primary variables (immune assays) is described in detail above

### **10.2.3 Handling of missing values/censoring/discontinuations**

In this study, discontinuation will usually be due to rejection occurring during the study protocol (TAC-WD/EVL). While unlikely as this trial is a small pilot study, patients lost to follow-up will be removed from the trial and analysis.

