## Glossary of terms

Assessment	A procedure used to generate data required by the study
Control drug	A study drug used as a comparator to reduce assessment bias, preserve blinding of investigational drug, assess internal study validity, and/or evaluate comparative effects of the investigational drug
Enrollment	Point/time of patient entry into the study; the point at which informed consent must be obtained (i.e. prior to starting any of the procedures described in the protocol)
Investigational drug	The study drug whose properties are being tested in the study; this definition is consistent with US CFR 21 Section 312.3 and is synonymous with "investigational new drug."
Medication number	A unique identifier on the label of each medication package in studies that dispense medication using an IVR system
Patient number	A number assigned to each patient who enrolls in the study. When combined with the center number, a unique identifier is created for each patient in the study.
Stage	A major subdivision of the study timeline; begins and ends with major study milestones such as enrollment, randomization, completion of treatment, etc.
Period	A minor subdivision of the study timeline; divides phases into smaller functional segments such as screening, baseline, titration, washout, etc.
Premature patient withdrawal	Point/time when the patient exits from the study prior to the planned completion of all study drug administration and assessments; at this time all study drug administration is discontinued and no further assessments are planned
Randomization number	A unique identifier assigned to each randomized patient, corresponding to a specific treatment arm assignment
Stop study participation	Point/time at which the patient came in for a final evaluation visit or when study drug was discontinued whichever is later
Study drug	Any drug administered to the patient as part of the required study procedures; includes investigational drug and any control drugs
Study drug discontinuation	Point/time when patient permanently stops taking study drug for any reason; may or may not also be the point/time of premature patient withdrawal
Variable	Information used in the data analysis; derived directly or indirectly from data collected using specified assessments at specified time points

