### 6.3.7 Study drug discontinuation and premature patient withdrawal

Subjects may be withdrawn from the trial at any time for any reason, either by choice or due to medical indications. Subjects who are non-compliant with study guidelines, medications and clinic examinations will be withdrawn from the study. The NU IRB may also discontinue the study at any point. The subjects will be fully informed of these actions. If patients are withdrawn prematurely, they will still be followed through the follow-up time period of the study as per standard medical care. These data are important to collect to determine differences in this group compared to those who completed the study.

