## 10.4 Sample size calculation

As this is an exploratory pilot study, we will enroll an initial 25 patients, 20 of who are expect to undergo TAC-WD/EVL. Of these, we expect 14-15 will not have AR during TAC-WD and 4-5 are expected to have AR, based on the initial EVL clinical trial. This will allow us to have preliminary information to proceed ahead to one of a few different directions, as outlined in Exploratory Objectives. Therefore, a power analysis was not needed for this pilot study.

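### Section 10.2.3 removes patients lost to follow-up from the analysis: it drops them from the success-rate denominator, discards samples already taken and can bias the reported rates

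*Combined protocol and SAP*

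**What the plan says.** Section 10.2.3 holds the whole missing-data policy. It expects most discontinuations to follow rejection and then turns to other losses: "While unlikely as this trial is a small pilot study", it says, "patients lost to follow-up will be removed from the trial and analysis". It makes no exception for samples or outcomes already recorded. Section 10.2.4 lists no supportive analysis.

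Section 6.3.7 deals with premature withdrawal. It includes patients who stop complying: "Subjects who are non-compliant with study guidelines, medications and clinic examinations will be withdrawn from the study". It continues: "If patients are withdrawn prematurely, they will still be followed through the follow-up time period of the study as per standard medical care". The reason follows: "These data are important to collect to determine differences in this group compared to those who completed the study". The Glossary describes the moment of premature withdrawal differently: "at this time all study drug administration is discontinued and no further assessments are planned".

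Section 7.3 makes the main efficacy measure the percentage of patients taken off tacrolimus in favour of everolimus without rejection or major complications. On numbers, section 10.4 says "we will enroll an initial 25 patients, 20 of who are expect to undergo TAC-WD/EVL", and of these "we expect 14-15 will not have AR during TAC-WD and 4-5 are expected to have AR".

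**The concern.** A patient who starts tacrolimus withdrawal and then disappears has already contributed information: the attempt itself, a rejection-free period up to last contact, and blood drawn before and perhaps after withdrawal. Removal from the analysis throws all of that away. It also makes the denominator depend on who stayed, which is harmless only if those who leave have the same outcomes as those who remain. Side effects, care elsewhere or poor compliance could each be linked both to leaving and to rejection.

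At stake are the headline success percentage, its complement the rejection rate, and the completeness of the marker data. Each rests on about 20 patients, and the pilot is meant to supply the figures for a larger trial.

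There is also a question of which rule applies. A patient who stops attending can be classed as withdrawn under section 6.3.7 or as lost under section 10.2.3, and the two classes are treated differently.

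**Working it through.** **Inputs.** Number starting withdrawal: n = 20 (section 10.4). Expected rejection: 20% (section 3). Expected split: 4-5 with and 14-15 without acute rejection (section 10.4). Number lost, L: not given, so assumed to be 1 to 3.

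**The plan's own figure.** 20 × 0.20 = 4 rejections, the lower end of 4-5, and 5/20 = 25% is the upper end. 20 × 0.80 = 16 without rejection, slightly above the stated 14-15. Of the stated combinations only 15 + 5 adds to 20, which is the split given under Figure 6. The expected counts are reproduced closely enough to use x = 4 and x = 5 observed rejections.

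**Effect of deletion.** With x observed rejections and L patients of unknown status, deletion reports x/(n − L). If everyone stays in the denominator, the lowest possible rate is x/n (no lost patient rejected) and the highest is (x + L)/n (all did).

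| Observed rejections | Lost (assumed) | Rate after deletion | Range with all 20 kept |
|---|---|---|---|
| 4 | 1 | 4/19 = 21.1% | 20% to 25% |
| 4 | 2 | 4/18 = 22.2% | 20% to 30% |
| 4 | 3 | 4/17 = 23.5% | 20% to 35% |
| 5 | 1 | 5/19 = 26.3% | 25% to 30% |
| 5 | 2 | 5/18 = 27.8% | 25% to 35% |
| 5 | 3 | 5/17 = 29.4% | 25% to 40% |

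The width of the range is L/20, or 5 percentage points per lost patient. The deletion figure always lies inside it. With x = 4 and L = 2, deletion is 22.2 − 20 = 2.2 points too high if neither lost patient rejected and 30 − 22.2 = 7.8 points too low if both did. The matching rejection-free share is 14/18 = 77.8% after deletion, against 14/20 = 70% to 16/20 = 80%. (Success in section 7.3 also requires freedom from major complications, which this illustration leaves aside.)

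**Samples.** Table 7-1 schedules blood at visits 3 to 7, with visit 3 marked as not mandatory. That leaves four mandatory scheduled samples, at visits 4, 5, 6 and 7. A patient lost after visit 4, 5 or 6 has given 1, 2 or 3 of them. Section 3 rests prediction on assays before and just after full withdrawal, so these are the samples that matter most. Section 10.2.3 does not mention samples; that they go is inferred from removal from the analysis.

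**The passages side by side.** Section 6.3.7: a patient who does not comply with clinic examinations is withdrawn, is still followed, and is compared with completers. Section 10.2.3: a patient lost to follow-up is removed. Glossary: after premature withdrawal nothing further is planned. For a patient who simply stops coming, these give different answers on follow-up and on use of the data. By contrast, section 9.1 lets the investigator go on using data collected before a patient revokes authorization, so someone who revokes permission may contribute more than someone who stops attending.

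**The case against.** The strongest reply is that this is an unpowered pilot with mainly descriptive clinical outcomes (section 10.3.1). Loss is expected to be rare, and follow-up is close: weekly laboratory tests in months 3 to 6 (section 7.4.4), telephone contact between visits (section 7.3) and regular coordinator contact (section 4). That stands, and it is why the point concerns a risk.

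Four stronger readings are tempting, and the documents do not support them.

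- *That section 10.2.3 directly contradicts section 6.3.7.* One speaks of patients lost, the other of patients withdrawn, and someone who cannot be reached cannot be followed. Section 6.3.7 also calls the data important to collect; it does not say that they must enter the main analysis. The conflict is confined to patients who fit both descriptions.
- *That losing one rejecter deletes 20-25% of the failure group (1/5 to 1/4).* Rejection is an endpoint. It ends that patient's participation, blood is taken at that time (section 7.3, Table 7-1), and section 10.2.3 treats it separately from loss. Only an unobserved rejection could go missing, and keeping the patient would not reveal it.
- *That the 30% upper bound means the stopping threshold is reached.* Section 10.3.2 acts on rejection that has been seen, and section 10.6 limits it to rejection believed to be due to the withdrawal. The upper bound counts two rejections that nobody observed, and nothing says that section 10.2.3 governs this monitoring. The missing denominator for that rule is a separate matter.
- *That a mixed model on available visits repairs the marker comparison.* Section 10.1 defines the groups by rejection outcome. A mixed model copes with missing marker values but cannot place a patient whose group is unknown.

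**Conclusion.** The point holds in a limited form. Section 10.2.3 is an explicit rule, not an omission, and nothing elsewhere offsets it. Followed literally, it shrinks the denominator of the efficacy percentage, discards up to three of four mandatory samples per lost patient, and replaces a range with a single figure that assumes lost patients fare like the rest.

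Bias in either direction is possible and is not shown. Its size depends on the number lost and their outcomes, neither of which the documents give. On the assumptions above, one to three losses leave 5 to 15 points of uncertainty that the reported rate would hide. The overlap between sections 10.2.3 and 6.3.7 and the Glossary is a wording problem that should be reconciled. The change is inexpensive and worth making, but this is not a fatal flaw in the pilot.

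**What to change.** Replace the sentence in section 10.2.3 with a rule on these lines:

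- Every patient who starts tacrolimus withdrawal stays in the denominator, and all data up to last contact are kept.
- A rejection observed before loss counts as a failure.
- Patients lost with unknown rejection status are reported as a separate count, and the success rate is shown with best-case and worst-case bounds.
- The marker comparison uses all available samples from patients with known outcome. A sensitivity analysis in section 10.2.4 then adds the lost patients, classed first as non-rejecters and then as rejecters.

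Reconcile sections 10.2.3 and 6.3.7 and the Glossary so that it is clear which description applies to a patient who stops attending, and what is done with that patient's data.

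**Cost.** No new visits or procedures. There are a few lines of text, one row of bounds in the efficacy table and one extra marker analysis. Using incomplete series means fitting the repeated-measures analysis in a form that accepts them, so the matching wording in the synopsis and in sections 10.2 and 10.3.3 should be aligned. The reported success rate will be wider, and may look slightly less favourable.

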### **10.2.4 Supportive analyses**

None – see Exploratory Objectives above

## **10.3 Analysis of secondary objectives**

Clinical endpoints as correlates for the success and failure of TAC-WD/EVL will serve as secondary endpoints. This will include but not be limited to the following at 6 months ( $\pm$  1 month) post-LT: liver allograft and renal function, EVL & TAC side effects, infectious/malignant complications, and patient/graft survival. At study end, all secondary endpoints will be statistically compared between those who succeed or fail TAC-WD/EVL.

### **10.3.1 Efficacy (secondary)**

All potential clinical endpoints will be recorded by case report form. Since this is a small pilot study, the clinical outcomes will be mainly descriptive in nature, e.g. rejection rate, medication side effect rate, liver/renal function outcomes, infectious complications, malignancy, and patient/graft survival. However, we will statistically compare these secondary endpoints between those who succeed or fail TAC-WD/EVL by standard continuous and categorical statistical tests.

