Clinically, we demonstrated in another study that LT recipients previously converted to SRL had higher percentages of PBMC Tregs compared to recipients on other IS therapies. This led to a prospective TAC to SRL conversion trial supported by the American Association for the Study of Liver Disease Career Development Award and Wyeth/Pfizer ([name]). Our aim was to determine if systemic phenotypic Tregs (CD4+CD25highFOXP3+), regulatory dendritic cells (DCregs: ILT3+/4+), and immunoregulatory proteogenomic signatures increase in LT recipients converted directly from TAC to SRL monotherapy. Twenty non-immune non-viremic LT recipients were successfully converted for renal dysfunction. The mean eGFR increased from 45.9±7.9 to 49.6±10.8 (p=0.003). Tregs increased significantly in PBMC, marrow [Fig. 2, from ref] and LT biopsy cultures. Biopsy immunohistology FOXP3:CD3 and CD4:CD8 ratios became significantly higher after conversion [Fig. 3, from ref]. Peripheral blood DCregs increased significantly (Fig. 2, p<0.01). Both pre- (TAC) and post- (SRL) conversion sera inhibited MLR proliferation, although only TAC sera suppressed Treg generation. 289 genes and 22 proteins, many of which are important in immunoregulatory pathways, were newly expressed after conversion [Fig. 4: from ref]. In conclusion, these studies demonstrated that TAC to SRL conversion increases systemic (blood, allograft, marrow) Tregs, blood DCregs and regulatory proteogenomic signatures in LT recipients. However, it is not known if this profile correlates with and predicts successful *early* mTOR-I use (i.e. TAC-WD/EVL) as in this proposal.

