## 4 Study design

Overall: Prospective, open-label pilot study comparing immunoregulatory assays in non-viremic LT patients undergoing TAC-WD/EVL. The patients will serve as their own control for assays, clinical, biochemical, and histological measures, and the groups will be divided and compared by the presence or absence of rejection before, during and after the TAC-WD/EVL phase (months 0-6 ( $\pm$  1 month)). We expect to find assay measures (primary objective) consistent with immunoregulation in patients who are successfully withdrawn from TAC compared to signs of immunoreactivity/lack of immunoregulation in those who fail TAC-WD due to rejection and require TAC reinstitution.

**Clinical Trial & Timelines (Figure 6 in Appendices):** Patients will be approached for study enrollment within six months before LT but can be enrolled up until 60 days post-LT. At transplant if possible, patients consented pre-LT will have donor spleen/lymph node cells and recipient lymph node/blood cells/sera cryopreserved. This will be collected for potential future studies of donor-specific immunoregulation and donor specific antibodies (funds not requested – see Exploratory Objectives). Post-transplant, patients will be treated as standard of care with the following protocol (no antibody induction): TAC therapy (target trough 7-10 ng/mL) +/- MPA between 1-3 g/d (Cellcept®, Myfortic® or generic alternate), corticosteroids (intravenous solumedrol 500 mg daily day 2, prednisone taper from 200 mg down to 20 mg daily at week 1, then slow taper to 5 mg daily by month 3). Patients not consent pre-LT will be approached within the first 60 days post-LT. At month 1 to 2 post-LT, study continuation criteria will be determined (see inclusion criteria). If met, EVL will be started (MPA discontinued if patient treated with this) and the EVL goal troughs will be 5-8 ng/ml and TAC 3-5 ng/ml . At 3 months ( $\pm$  1 month) post-LT, patients on stable TAC + EVL meeting continuation criteria will undergo the TAC-WD/EVL phase. TAC will be reduced by 50% of daily dose. After two weeks, if liver enzymes are stable, TAC will be reduced 50% each week and discontinued at month 4 ( $\pm$  1 month) post transplant, if criteria are met. From month 4-6 ( $\pm$  1 month), the patients will be on EVL therapy alone (trough 5-8 ng/ml) with stable prednisone 5 mg/day until study end (6 months ( $\pm$  1 month)) or rejection (expected in ~20%).

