Peripheral blood bioassays will be performed pre-TAC-WD (1 to 2 months and 3 months ( $\pm$  1 month)), immediately pre-TAC-WD (4 months ( $\pm$  1 month)), 2 weeks post-TAC-WD (4.5 months ( $\pm$  1 month) post-LT), at biopsy-proven rejection in any phase of the study (before or after TAC-WD phase), and at 6 months ( $\pm$  1 month) post-LT (Timeline Figure 6). We will also store extra blood samples (funds not requested – See Exploratory Objectives). Liver biopsies for standard histology will be performed only for cause at the time of rejection and not required by the protocol – extra tissue placed in RNAlater will be collected (funds not requested). The blood biomarkers will be compared between the groups (AR vs. no AR). Additionally, the patients will be monitored as standard of care with clinical laboratory tests (CBC, liver/renal function tests, IS trough levels) for other respective secondary endpoints (hematologic, liver/renal function) every 1-2 weeks. Clinical laboratory tests for other endpoints (hyperlipidemia- lipid profiles, diabetes- HbA1C, proteinuria- urine protein/creatinine) will be performed pre-EVL addition and at 6 months ( $\pm$  1 month) post-LT, all per our standard of care. Routine clinic visits will occur per standard of care (1, 2, 3, 4 & 6 months) to monitor for side effects and document any adverse events, in addition to our research coordinators maintaining close communication with the patients. The study will be completed at 6 months ( $\pm$  1 month) post-LT, which will include final assessments of clinical and laboratory outcomes. Case report forms and electronic databases documenting all immune assay results and clinical data/outcomes will be utilized for all endpoint comparisons.

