### Criteria for Study Continuation and EVL addition (1 to 2 months post-LT):

1. Currently on TAC + prednisone +/- MPA therapy with no contraindication to starting EVL (i.e. wound infection; significant proteinuria (urine prot/cr ratio  $\geq 1.0$ ), hepatic artery thrombosis/stenosis, cytopenias (WBC  $< 1.5$ , ANC  $< 1.0$ , Platelet  $< 30$ , Hemoglobin  $< 7$ ), other deemed by investigator)
2. No more than 2 rejection episodes or 1 steroid-resistant rejection requiring lymphodepletion therapy
3. No active biliary, infectious, or malignant process
4. eGFR  $\geq 30$  ml/min/1.73m^2
5. No significant liver function abnormalities (Direct bilirubin, AST/ALT, Alkphos  $\geq 2x$  elevated)
6. If on current or prior antiviral therapy, HBV and HCV viral load should be undetectable
7. No combined transplantation (e.g. should be primary liver transplant alone)

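### Section 10.3.1 commits to comparing 6-month renal function between success and failure but specifies no baseline adjustment, although pre-EVL eGFR is already collected

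*Combined protocol and SAP*

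**What the plan says.** Section 3.2 and Section 10.3 list renal function at 6 months among the clinical endpoints to be compared between patients who succeed and patients who fail withdrawal. Section 10.3.1 first limits the ambition: "Since this is a small pilot study, the clinical outcomes will be mainly descriptive in nature". It then commits to testing all the same: "we will statistically compare these secondary endpoints between those who succeed or fail TAC-WD/EVL by standard continuous and categorical statistical tests". That is the whole method for these endpoints.

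Other sections point towards a within-patient reference:

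- Section 4 states: "The patients will serve as their own control for assays, clinical, biochemical, and histological measures". No analysis section turns this into a method for renal function.
- Section 7.3 makes improvement in tacrolimus side effects, renal ones included, an efficacy endpoint in patients successfully withdrawn. Improvement cannot be read from a month-6 value alone.
- Section 10.2 does specify paired tests and repeated-measures ANOVA, but only for the cell data.

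The baseline data exist. The continuation criteria at 1 to 2 months include an eGFR threshold, checked before everolimus is added, and Section 4 has renal function tested every 1–2 weeks as standard care.

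Section 10.4 gives the size: "we will enroll an initial 25 patients, 20 of who are expect to undergo TAC-WD/EVL", with 14–15 expected to be free of rejection and 4–5 expected to reject. Section 10.1 confirms that there is no randomisation and that the groups follow from rejection.

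**The concern.** Preserved renal function is the clinical reason for withdrawing tacrolimus (Section 1), and Section 7.4 sets it against the rejection risk. A reader will therefore look at the 6-month renal comparison even though it is secondary.

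With 4–5 patients in the smaller group and no randomisation, one or two patients with an unusual starting eGFR can move that group's mean appreciably. A comparison of month-6 values alone cannot separate this from anything that happened after everolimus was added. It also leaves in the error term the variation between patients that was already present at baseline.

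An open method raises a further issue. Raw values, changes and adjusted values can give different answers in 20 patients, and the plan does not say which one counts.

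**Working it through.** **Plan's own figure.** No SD, SE, effect size or power is given for the renal comparison, so there is nothing to reproduce beyond the group split. Section 10.4 gives 14–15 versus 4–5, and the Figure 6 footnote gives 15 versus 5. The 20% rejection rate in Section 3 would give 20 × 0.20 = 4 and 20 × 0.80 = 16. I use 15 versus 5.

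**Step 1: the only correlation the documents yield.** For the group's earlier tacrolimus-to-sirolimus conversion study, Section 1 reports: "The mean eGFR increased from 45.9" ± 7.9 to 49.6 ± 10.8, p = 0.003, in 20 patients. Assuming a paired t-test:

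- t on 19 df for two-sided p = 0.003 is 3.40.
- Mean change = 49.6 − 45.9 = 3.7.
- SD of change = 3.7 / 3.40 × √20 = 4.87.
- r = (7.9² + 10.8² − 4.87²) / (2 × 7.9 × 10.8) = 0.91.

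Rounding of p gives a range of 0.905–0.917. Reading the ± values as standard errors gives r = 1.04, which is impossible, so they are taken as SDs.

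**Step 2: SE without adjustment.** With an assumed month-6 SD of 10.8:

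SE = 10.8 × √(1/15 + 1/5) = 5.58.

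**Step 3: SE with ANCOVA.**

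- No systematic baseline difference, allowing for estimation of the slope (N = 20): SE = 10.8 × √(1 − r²) × √[(1/15 + 1/5)(1 + 1/16)] = 5.75 × √(1 − r²).
- Observed baseline difference of 1 SD: SE = 10.8 × √(1 − r²) × √(1/15 + 1/5 + 1/18) = 6.13 × √(1 − r²).

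| Assumed r | ANCOVA SE, balanced | Change from 5.58 | ANCOVA SE, 1-SD imbalance | Change from 5.58 |
|---|---|---|---|---|
| 0.2 | 5.63 | 1% larger | 6.01 | 8% larger |
| 0.3 | 5.48 | 2% smaller | 5.85 | 5% larger |
| 0.5 | 4.98 | 11% smaller | 5.31 | 5% smaller |
| 0.7 | 4.11 | 26% smaller | 4.38 | 21% smaller |
| 0.91 | 2.38 | 57% smaller | 2.54 | 54% smaller |

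Break-even in the balanced case: 1 − r² = 1/1.0625, so r = 0.24. Splits of 16/4 and 14/4 give the same percentages within about 2 points.

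A simulation (20,000 runs per setting) agrees for balanced baselines: SE ratios of 0.89, 0.74 and 0.45 at r = 0.5, 0.7 and 0.9. With a true 1-SD imbalance, where the observed imbalance varies around 1 SD, the ratios are 0.99, 0.81 and 0.49. At r = 0.5 the gain then nearly disappears.

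**Step 4: effect on the estimate itself.** If the groups differ by 0.5 SD at baseline, adjustment moves the estimated difference by r × 10.8 × 0.5: 2.7 units at r = 0.5, 3.8 at 0.7 and 4.9 at 0.9. The whole mean gain in the earlier conversion study was 3.7.

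**The case against.** **The plan does not prescribe an unadjusted test.** A reader might infer that it does. Section 10.3.1 leaves the test open, ANCOVA could count as a standard method for continuous data, and the own-control statement in Section 4 points towards baseline. This stands: the supportable statement is that no baseline adjustment is specified.

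**The stakes are low.** The comparison is secondary and mainly descriptive, and Section 10.5 says power was not considered necessary. This also stands and limits the weight of the point. It does not remove it, because the same section commits to a statistical comparison.

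**The size of the gain is borrowed.** The 0.91 and the SD of 10.8 come from patients converted successfully for renal dysfunction, in what Section 10.2 calls late conversion. Here the baseline falls 1 to 2 months after transplant and the sample includes rejectors. This stands, so the table runs down to a correlation of 0.2.

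**Baseline differences are not shown.** A reader might infer that an unadjusted difference would mostly reflect who started with better kidneys. Nothing in the documents links starting eGFR to rejection, so the most that can be said is that it may.

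**Adjustment is not only a gain in precision.** The groups are formed by a later outcome, so adjustment also changes the quantity estimated. Patients who fail have tacrolimus reinstated, which baseline adjustment cannot undo. The tacrolimus target is already lowered when everolimus starts (Sections 4 and 6.2), so a pre-EVL baseline covers that reduction as well as the withdrawal; a month-3 baseline would answer a narrower question. These points stand, and they call for cautious interpretation and a stated baseline.

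**Month-6 values in failures are not secured by a study visit.** Section 7.3 ends a patient's study at rejection. Section 6.3.7 keeps prematurely withdrawn patients under standard-care follow-up, so a value should usually exist, but the plan does not say that it will be used.

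**Conclusion.** The point holds as a gap in specification. The plan promises a 6-month renal comparison between two small, non-randomised groups and names no baseline term, although a baseline is already collected. A month-6-only comparison may reflect starting differences and is probably less precise than it could be.

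At 15 versus 5 and an assumed SD of 10.8, the SE falls by 11% to 57% over correlations of 0.5 to 0.91. The reduction is smaller with baseline imbalance, and there is none below about r = 0.25. The upper end assumes that a correlation from late, successful conversions, derived on the assumption of a paired t-test, carries over. It probably does not in full.

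A reader might also infer that the gain is certain or free. The documents give no correlation for this setting, so its size is not established. Free applies to data collection only: one of 18 residual degrees of freedom is spent. The importance is modest, since this is a secondary comparison in an unpowered pilot.

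**What to change.** Add to Section 10.3.1:

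- Month-6 eGFR is analysed by ANCOVA with the pre-EVL eGFR as covariate. The adjusted difference between success and failure is reported with a 95% CI, together with each patient's change from baseline.
- The result is described as an association, because the groups are formed by rejection.
- For patients whose study ended at rejection, the standard-care month-6 eGFR (follow-up under Section 6.3.7) is collected and used. The number without a value is reported by group.

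The cost is a few sentences, one residual degree of freedom (18 to 17) and retrieval of routine laboratory values for the expected 4–5 failures. No extra visit or sample is needed. If the correlation turns out low or the groups differ widely at baseline, the adjusted interval may be slightly wider than the unadjusted one. Showing individual changes lets the reader see this.
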